CONTROLLED PHONATION AND VOCAL REST PROGRAMS AFTER ACUTE VOCAL EXERTION IN HEALTHY ADULTS

NCT03762993

07/22/2020

APPLICATION NARRATIVE FORM

Purdue University, Institutional Review Board

A. PROPOSED RESEARCH RATIONALE

Roughly 17.9 million adults in the United States are affected by voice disorders annually.¹ These disorders reduce quality of life and social interaction.² Voice disorders represent a significant financial burden, costing hundreds of millions of dollars in medical bills and resulting in an average of what is estimated to be as many as 39.2 work days per year.³ Although the etiologies of voice disorders vary, speakers with voice problems consistently report vocal fatigue and increased effort to speak as the first symptoms. These speakers are often advised to cease voice use partially or completely, however, this may not be realistic given their occupation and the high cost to quality of life by not speaking.⁴ The question then becomes, what should be done to mitigate the negative symptoms of voice problems when they occur, both to ease subsequent vocal function and to avoid eventual voice disorders.

In other anatomical subsystems, the idea of “cool down” following exertion is common. Data from multiple tissue types suggest that cool down following acute trauma may improve recovery. Emerging data suggest that a vocal cool down, may have a beneficial effect on vocal fold wound healing.⁵ This work has primarily been done on animal models, however, preliminary data gathered in human subjects suggests that some individuals benefit from a cool down following vocally tiring events.⁶ However, this question has not been systematically studied investigated in a rigorous manner that also enables us to understand the underlying mechanisms of this beneficial effect.

The proposed study will examine the effects of vocal cool down following exertion on voice measures and respiratory kinematics. Each speaker will also participate in a vocal rest experiment so we can compare cool down with vocal rest. Specifically, we seek to determine if a vocal cool down can mitigate the negative effects of a vocally tiring task as compared to vocal rest. We will assess voice measures and respiratory kinematics repeatedly to identify underlying mechanisms.

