The study design will be a within-participant, repeated measures design. Once subjects are screened (see below), they will be scheduled to participate on two consecutive days. The procedures will be similar on both day. In brief, voice and respiratory measures will be collected on each day. Subjects will then perform a vocal exertion task and voice and respiratory measures will be collected again. The subjects will perform a cool down or vocal rest. Voice and respiratory measures will be collected again, followed by a second vocal exertion task and re-collection of voice and respiratory measures.

Because this study meets the NIH definition of a clinical trial, this study will be registered on ClinicalTrials.gov. A description of this clinical trial will be available on <http://www.ClinicalTrials.gov>, as required by U.S. law, once the IRB is approved.

B. SPECIFIC PROCEDURES TO BE FOLLOWED

The proposed methodologies are routinely used in our laboratories. All proposed methodologies have been previously approved by the Purdue IRB. In addition, all devices utilized in this study are commercially available and will be used in accordance with their approved label.

[figure not shown]
Protocol and Research Design:

Phone Screening and scheduling: verbal consent will be obtained before any questions will be asked over the phone. Once consent is obtained, screening questions will be asked (Document A). If subjects meet exclusion

criteria they will not be scheduled. If subjects are willing and able to participate, they will be asked to come back to the lab on two consecutive days at roughly the same time of day and will be scheduled.

Day 1: Informed consent will be obtained. Next, participants will complete a questionnaire (Document B) asking about current health status, medical history, medications, and occupational voice use. Then, participants will complete the Vocal Fatigue Index (Document C), the Vocal Handicap Index (VHI) (Document D) and the Reflux Symptom Index (RSI, Document E). Overall, these data will provide us a complete understanding of each participant's medical history, voice use, perception of voice and occupational voice needs. Then subjects will be scheduled for the following procedures if they are willing and available. Partial payment will not be provided if they are unwilling or unable to participate in the following procedures.

A schematic of the research design is shown below:

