Respiratory kinematic data will also be collected. To collect these data, respiratory bands will be placed around the subject's rib cage and abdomen. These bands will be attached with tape over clothing and do not pose any risk to the participant. Participants will be seated and asked to remain relatively still throughout these procedures. Next calibration will be completed. In order to achieve calibration, each participant will be asked to perform the following tasks while the movements of the chest wall and abdomen are recorded; quiet breathing, breathing while thinking a sentence silently, breathing in and out as much as possible, pulling the stomach in and pushing the stomach out as much as possible. The breathing tasks will be performed into a cardboard tube attached to a filter which is placed in the subject's mouth. These tubes are disposed of following each use and the filters disinfected. In addition, nose clips may be used during these tasks and are again disposed of after each use. Following calibration, subjects will be asked to read prepared sentences while wearing the respiratory bands.

In summary, spirometry will be collected one time per day, on both days. Videostroboscopy, voice measures and respiratory measures will be collected at 4 different times on each day. These times are (1) before the vocal exertion (see below; (2) after the vocal exertion (3) before vocal exertion (4) after vocal exertion.

Vocal Exertion Task: For this task, subjects will produce loud sounds for 15 minutes. Subjects will complete a vocal exertion task two times on each day.

Measures: Videostroboscopy, voice measures, and respiratory kinematics will be reobtained after the vocal exertion task.

Cool Down versus Vocal Rest: Participants will be counterbalanced to cool down or vocal rest such that each participant will complete both on different days. Each will take less than 15 minutes. For vocal rest, subjects will not speak. For cool down, subjects will complete voice exercises. These exercises are commonly utilized in clinical settings in order to help patients reduce throat tension and speak more efficiently. The exercises involve speaking and singing long vowels and pitch glides both with and without a straw. In addition, participants will hum and speak sentences with specific consonants (e.g. m and p). Each participant will be provided a new straw.

Measures: Videostroboscopy, voice measures, and respiratory kinematics will be obtained.

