Vocal Exertion Task: Next, subjects will complete the second vocal exertion task for the same duration or shorter duration as the first task.

Measures: Videostroboscopy, voice measures, and respiratory kinematics will be obtained.

C. SUBJECTS TO BE INCLUDED

Participants will include males and females > 18 years with normal speech and language. Inclusion and exclusion criteria are listed below.

Exclusion criteria: Individuals will not be included in this study if they report cognitive impairments or disorders, craniofacial disorders (i.e., cleft palette or submucosal cleft), head and neck cancer, hearing difficulties, or have dentition problems or dentures which limit laryngeal imaging. Subjects will also be excluded if they report a gag reflex when they brush their teeth or refuse to undergo laryngeal imaging.

Inclusion criteria: Participants must be within the appropriate age range (18-65 years at the time of study) to participate in this study. They must score $\geq 80\%$ for their age, weight, height and race on forced vital capacity and forced expiratory volume in 1.0 second on spirometry. In addition, the investigators must be able to obtain an image of the individual's larynx using rigid endoscopy to ensure that no gross laryngeal pathology is present. The presence of any pathology will preclude participation.

If any pathology is observed suggestive of an underlying condition, the subject will be referred back to their physician and will not be included in the study.

Participant availability and plan for dropout: We do not anticipate any difficulty in recruiting adults. We will recruit participants through fliers posted on campus and surrounding communities, ads in Purdue Today or similar newsletters, word of mouth, email, or phone. If participants drop out of the study before the end, they will be paid a partial payment and we will recruit a new participant to replace them.

D. RECRUITMENT OF SUBJECTS AND OBTAINING INFORMED CONSENT

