J. STATISTICAL ANALYSIS PLAN

Statistical analysis will be conducted using SAS (Version 9.4, 2013). Power analysis indicates an N of 30 subjects will be sufficient to answer study questions with reasonable statistical power. Dependent measures will be analyzed using linear mixed effect models. Fixed factors included in the statistical model will include time (baseline, post exertion task 1, post restorative strategy, post exertion task 2) and restoration strategy (controlled phonation or vocal rest). A time and restoration strategy interaction will also be included in the model. Participant will be included as a random factor in order to control for individual variation. Alpha level for significance will be set at $p < .05$. Tukey HSD tests will be used on post-hoc comparisons. In addition, Cohen's d for repeated measures will be calculated on significant post-hoc comparisons using the Cohen's d calculator for repeated measure designs developed by Psychometric.de (https://www.psychometrica.de/effect_size.html).

References

1. Bhattacharya, N. The prevalence of voice problems among adults in the United States. *The Laryngoscope* **124**, 2359–2362 (2014).
4. Rousseau, B. *et al.* Compliance and quality of life in patients on prescribed voice rest. *Otolaryngol.-- Head Neck Surg.* **144**, 104–107 (2011).
5. Branski, R. *et al.* Dynamic biomechanical strain inhibits IL-1beta-induced inflammation in vocal fold fibroblasts. *J. Voice* **21**, 651–60 (2007).
6. Verdolini Abbott, K. *et al.* Vocal exercise may attenuate acute vocal fold inflammation. *J. Voice* **26**, 814.e1–13 (2012).

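### Section J names no comparison that estimates the cool-down-versus-rest difference in change, and its single error term is right only without day-to-day variation or serial correlation

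*Combined protocol and SAP*

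**What the plan says.** The aim in Section A is to "determine if a vocal cool down can mitigate the negative effects of a vocally tiring task as compared to vocal rest". Section B has four assessments on each of two days, with participants "counterbalanced to cool down or vocal rest such that each participant will complete both on different days".

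Section J fits a linear mixed model with time (baseline, post exertion task 1, post restorative strategy, post exertion task 2) and strategy as fixed factors. It adds that "A time and restoration strategy interaction will also be included in the model". On the random part it says: "Participant will be included as a random factor in order to control for individual variation". It lists no day or session term and no residual covariance structure. The follow-up is given as "Tukey HSD tests will be used on post-hoc comparisons", without saying which pairs. Cohen's d is then computed for the pairs that reach significance. Alpha is .05 and N is 30.

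**The concern.** The question in Section A concerns change on the cool-down day against change on the rest day. Section J does not say which output answers it, at which time point, or against which reference. A significant interaction would leave the answer to pairs chosen after the data are seen. A non-significant result would leave no planned effect estimate at all, because d depends on significance and no interval is planned.

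The second issue is the error term. Strategy and day coincide within a participant, so comparisons between strategies are comparisons between days. A model with only a participant intercept uses one pooled residual both for these and for changes within a day. Day-to-day variation affects the two kinds of comparison differently.

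**Working it through.** **Inputs.** From Sections B and J: 30 participants, 2 days, 4 times per day, alpha .05 (two-sided assumed). The documents give no power figure, effect size, SD, day variance or within-day correlation, so those below are assumptions shown as ranges.

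**1. The plan's own figure.** N = 30 cannot be reproduced. For a two-sided paired comparison it fits a standardised effect of 0.50 to 0.53 at 80% power, 0.53 to 0.57 at 85%, or 0.58 to 0.62 at 90%. The stated N therefore does not show which comparison was intended.

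**2. What the planned tests estimate.**
- The interaction has (4 − 1) × (2 − 1) = 3 df. It validly tests whether change differs between strategies, but not when or in which direction. An effect of 1.06 residual SD only after restoration gave 85.4% power; the same effect only after exertion task 2 gave 85.5%.
- If the Tukey family is all eight cells, there are 8 × 7 / 2 = 28 pairs: 4 same-time between strategies, 12 within a strategy and 12 mixed. A difference in change needs at least four cells, so none of the 28 is one. The critical t is 3.06, against 1.97 unadjusted.
- The strategy main effect averages all four times. A benefit δ at both later times appears as (0 + 0 + δ + δ)/4 = δ/2, and at one later time as δ/4.

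**3. Error term under day variance.** Let s²e be the residual variance and s²d the participant-by-day variance. The participant-only residual has 29 × 7 = 203 df: 29 with expectation s²e + 4s²d and 174 with s²e. Its expectation is (29(s²e + 4s²d) + 174s²e)/203 = s²e + (4/7)s²d. The main effect needs s²e + 4s²d, a same-time strategy pair s²e + s²d, and the interaction s²e. With s²e + s²d = 1:

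| Day share | Residual used | Main effect needs | Interaction needs | Main-effect false positives (simulated) | Interaction error (simulated) |
|---|---|---|---|---|---|
| 10% | 0.957 | 1.3 | 0.9 | 9% | 4% |
| 30% | 0.871 | 1.9 | 0.7 | 18% | 2% |
| 50% | 0.786 | 2.5 | 0.5 | 27% | 1% |

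Unadjusted same-time strategy pairs run at about 6 to 9%. With s²d = 0 and no serial correlation, all are about 5%.

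**4. Serial correlation, no day variance.** At AR(1) 0.5, the participant-only main effect has about 21% false positives and the interaction about 2%. Now take two cool-down-minus-rest contrasts: A (post restorative strategy) and B (post exertion task 2), each minus the mean of that day's baseline and post exertion task 1. At AR(1) 0.3, 0.5 and 0.7, Holm error over A and B is:
- mixed model with a session term: 6.7, 7.7 and 8.8%;
- participant-only model: about 5, 4 and 2%;
- one-sample t on per-participant contrast values (29 df): 4.4 to 4.8% throughout.

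**5. Power.** Effects were scaled to noncentrality 7.92, which gives the interaction 64.0% on F(3, 203). Holm on 29 df, no day variance:

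| Assumed benefit | Holm, 29 df | Difference from 64.0% |
|---|---|---|
| Equal at both later times | 68.2% | +4.2 |
| One time only | 62.6% | −1.4 |
| Fades to half | 69.1% | +5.1 |
| Fades to a quarter | 67.8% | +3.8 |

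With total within-participant variance fixed and day shares of 30% and 50%, the planned participant-only interaction has 70% and 76%. Session-model Holm has 85.8% and 94.9% (equal benefit) or 82.2% and 93.3% (one time). Deducting a full 4 points for the 29-df test leaves about 82% and 91%, or 78% and 89%.

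**The case against.** Section J does plan outputs with time, direction and size: Tukey pairs and Cohen's d. A reader might infer that the plan yields none of these, and that would be wrong. They come only for significant pairs, however, and without an interval.

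The same-time strategy pairs are also closer to the question than the pair count suggests. Under counterbalancing, both pre-strategy times should have no expected strategy difference. The pair after restoration then has the same expectation as A, and the pair after exertion task 2 the same as B. Without day variance the pair is more precise: 2s²e/30 against 2 × (1 + 1/4 + 1/4)s²e/30 = 3s²e/30. With day variance its variance is 2(s²e + s²d)/30, which passes that of A once s²d exceeds s²e/2. This stands, but the plan does not name these pairs, and its error for them is too small if days vary.

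Three stronger readings are tempting:
- That the plan will judge benefit by the inflated main effect. Section J does not name it as the test of benefit.
- That the planned error is wrong as a matter of fact. That depends on variances the documents do not give, and for the interaction the harm is lost power rather than false positives.
- That strategy is biased by day. With balanced order the average day effect cancels; what remains is unmodelled noise.

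The averaged reference is also a choice. Change from post exertion task 1 alone matches the idea of mitigation more directly, but its Holm power in the session model, with no day variance, is only 53 to 58%.

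**Conclusion.** The concern holds in a conditional form and should be acted on. That no named comparison estimates the difference in change follows from the text and needs no assumption. The error-term defect depends on day variance or within-day serial correlation. Either is plausible with four measurements in one sitting on each of two days, but neither is quantified, so the false-positive figures are ranges and not predictions.

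The case for change is a pre-specified, interpretable estimate with valid error. A reader might infer a large power gain from naming contrasts, and the figures do not support that. Without day variance the change is small and can be negative. With material day variance the named contrasts beat the planned interaction, but most of that comes from using the right error: the interaction with a session term also reaches 81% and 93% at day shares of 30% and 50%. All power figures assume complete, balanced data and the four benefit patterns shown.

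**What to change.** - Keep the fixed effects and the interaction. Add a participant-by-day random effect to the mixed model; as each participant does one strategy per day, in SAS this is RANDOM INTERCEPT STRATEGY / SUBJECT=participant.
- Pre-specify contrasts A and B for each measure (time weights −1/2, −1/2, 1, 0 and −1/2, −1/2, 0, 1; cool down minus rest). State the reason for the reference: both times precede that day's strategy, and averaging them lowers variance. Give change from post exertion task 1 alone as a supporting estimate, because the average removes only half of a between-day difference in the first exertion response.
- Make the primary analysis the 30 per-participant values of each contrast: one-sample t test on 29 df, its own 95% confidence interval, and Holm over A and B (smaller p against 0.025, then the larger against 0.05). State that Holm decides if an unadjusted interval disagrees. This analysis assumes nothing about within-day correlation. The session-term model should not decide A and B, given its 7 to 9% Holm error under serial correlation.
- State that the strategy main effect is not the test of benefit, and list the Tukey pairs.
- Section B says "subjects will complete the second vocal exertion task for the same duration or shorter duration as the first task". Report that duration for each day beside B, as description.

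**Cost.** SAP wording, one RANDOM term, a short derivation of contrast values, and a record of second-task duration if none is kept. The analysis commits to named contrasts, and the 29-df test gives up 3 to 4 points of power against the session model if errors are independent. A participant missing an assessment that a contrast uses drops out of that contrast. Multiplicity across the many measures is not addressed and needs its own decision.

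### Participant is the only random factor in Section J: if values correlate within a day, the time-by-strategy test loses power and the strategy main effect is tested too leniently

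*Combined protocol and SAP*

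**What the plan says.** The aim in Section A is comparative: "we seek to determine if a vocal cool down can mitigate the negative effects of a vocally tiring task as compared to vocal rest".

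Section B sets the data structure. Participants are "asked to come back to the lab on two consecutive days at roughly the same time of day". For the measures, "Videostroboscopy, voice measures and respiratory measures will be collected at 4 different times on each day". For the strategies, "Participants will be counterbalanced to cool down or vocal rest such that each participant will complete both on different days".

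Section J specifies a linear mixed model in SAS. Its fixed effects are time (four levels: baseline, after the first exertion, after the strategy, after the second exertion), strategy (two levels) and their interaction. On random effects it says only: "Participant will be included as a random factor in order to control for individual variation". It names no participant-by-day or participant-by-strategy term, no residual covariance structure and no degrees-of-freedom method. For follow-up comparisons, "Tukey HSD tests will be used on post-hoc comparisons". On size, "Power analysis indicates an N of 30 subjects will be sufficient to answer study questions with reasonable statistical power".

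**The concern.** The eight values per participant fall into two day clusters of four. Strategy is applied to whole days and time varies inside a day, which is a split-plot layout. Because each strategy has its own day, participant-by-day and participant-by-strategy are the same unit. A lone participant intercept treats all eight values as equally correlated, whichever day they come from.

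That holds only if a participant's day-to-day state and the daily instrument set-up add nothing. Section B has the respiratory bands, calibration, headset microphone and airflow mask used on each day, so some shared day-level error is plausible. This is an inference; the documents do not quantify it.

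If such variation exists, the two strategy-related tests go wrong in opposite directions. Time-by-strategy matters most, because two of the four times come before the strategy is applied. That test becomes conservative, so a real benefit of cool down is easier to miss with N fixed at 30. The strategy main effect answers the question less directly, but it is a named factor tested at .05 and would be declared significant too often.

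**Working it through.** **The plan's own figure.** N = 30 cannot be reproduced. Section J gives no effect size, standard deviation, correlation, target test or numeric power. The 80% used below is a reference point of this review, not a claim in the plan.

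**Inputs.** From the documents: 30 participants (dropouts replaced), 2 days, 4 times per day, alpha .05. This gives 30 × 2 × 4 = 240 values, taken as balanced. Assumed: r = s2d/s2e, where s2d is the participant-by-day variance and s2e the within-day residual variance.

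**Error terms.** The participant-only residual has 240 − 8 − 29 = 203 df. It pools two lines:
- participant-by-day: 29 df, expectation s2e + 4·s2d
- within-day: 174 df, expectation s2e

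Pooled expectation = s2e + (29 × 4/203)·s2d = s2e + 0.571·s2d.

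The errors actually needed are:
- strategy: s2e + 4·s2d
- time-by-strategy: s2e
- strategy contrast at one time: s2e + s2d
- contrast between two times on one day: s2e

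For any s2d above zero, the pooled term is too small for strategy and too large for time-by-strategy. At r = 1 the ratio of needed to pooled error is 5/1.571 = 3.18 for strategy and 1/1.571 = 0.64 for time-by-strategy.

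**Rates under the planned model**, from simulating the exact chi-square mixture. The interaction effect has noncentrality 11.15, which gives 80% power on 3 and 174 df.

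| r | 0 | 0.05 | 0.1 | 0.25 | 0.5 | 1 |
|---|---|---|---|---|---|---|
| Same-day correlation after removing participant, r/(1+r) | 0 | 0.05 | 0.09 | 0.20 | 0.33 | 0.50 |
| Time-by-strategy power, % | 80 | 79 | 78 | 74 | 67 | 54 |
| Time-by-strategy type I error, % | 5.0 | 4.5 | 4.1 | 3.1 | 1.9 | 0.8 |
| Participants needed for 80% power | 30 | 31 | 32 | 34 | 38 | 46 |
| Strategy type I error, % | 5.0 | 6.9 | 8.8 | 13.8 | 19.9 | 27.1 |
| Same-time strategy contrast, unadjusted, % | 5.0 | 5.2 | 5.5 | 6.1 | 7.0 | 8.3 |
| Within-day contrast, unadjusted, % | 5.0 | 4.7 | 4.4 | 3.6 | 2.7 | 1.5 |

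Tukey familywise error over all 28 cell pairs moves little: 5.0% at r = 0, then 5.2, 5.5 and 6.0% at r = 0.25, 0.5 and 1.

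**Check on full simulated data.** With 20,000 data sets per ratio, the planned model gave 4.7 / 6.9 / 8.7 / 13.9 / 20.1 / 27.3% for strategy and 5.1 / 4.6 / 4.2 / 3.1 / 1.9 / 0.8% for time-by-strategy. With participant-by-day added, both tests were at 4.7–5.2% at every ratio. A separate run of 40,000 trials per setting showed interaction power back at 80%.

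**Other covariance patterns.**
- Serial (AR(1)) within-day correlation of 0.2 / 0.4 / 0.6 / 0.8, planned model: strategy type I error 10.0 / 16.7 / 25.0 / 35.0%; time-by-strategy 4.2 / 3.0 / 1.7 / 0.3%. The directions are the same.
- Participant-by-time variance s2pt: its line has 87 df and expectation s2e + 2·s2pt, so the pooled residual gains (87 × 2/203)·s2pt = 0.857·s2pt. Strategy is then too lenient only if 4·s2d > 0.571·s2d + 0.857·s2pt, that is, if s2pt < 4·s2d. Time-by-strategy stays conservative.

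**The case against.** **The harm depends on an unknown variance.** At r = 0 both planned tests are correctly sized. Consecutive days at about the same hour may keep day variance low, and at r = 0.05 to 0.1 interaction power falls by only 1 to 2 points. This stands as a limit on size. The direction does not depend on the value of r.

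**Section J is brief rather than wrong.** It does not say that participant is the only random effect, and SAS would allow a REPEATED covariance structure. That is true, but no such structure is specified, and an analyst following the text would fit the participant intercept alone.

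**The largest figure belongs to the less relevant test.** This is fair. The 27.1% concerns the strategy main effect and should not set the weight of the point. For time-by-strategy the error is conservative and creates no excess false claims, and Tukey familywise error barely moves. What remains is lost power on the central question.

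**One random term is a partial repair.** This also stands. Under AR(1), the day intercept leaves the interaction test slightly liberal (5.4–6.5%). With participant-by-time variance at half the residual and no day variance, the two-term model gives about 0.9% for time-by-strategy and 12% for time, against 1.1–1.2% and 13% for the planned model, so it repairs almost nothing there. If software bounds the day variance at zero, then at r = 0 the bound is reached in about 53% of trials. Strategy type I error is then 3.9% and interaction 5.3%, so the nominal 5% is approximate near zero.

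**Conclusion.** The concern holds and should be fixed. Under the plan as written, any positive participant-by-day variance means that strategy and time-by-strategy are both tested against the wrong error. The consequence that matters is lost power for time-by-strategy: from negligible at weak same-day correlation to 26 points (80% to 54%) when day variance equals residual variance. Inflation of the strategy main effect is secondary but appears early, at 8.8% for r = 0.1.

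The direction for time-by-strategy is firm. It follows from the mean squares and persists under AR(1) and with participant-by-time variance. The direction for strategy requires participant-by-time variance below four times day variance. The size rests on an assumed r, balanced data from 30 participants and a reference power of 80%; none of the variances can be taken from the documents.

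**What to change.** In Section J, replace the random-effects sentence with: *Participant and participant-by-day will be included as random effects (SAS PROC MIXED, Kenward-Roger degrees of freedom). Tukey comparisons will be taken from this model.*

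Add a statement that this term does not by itself handle serial within-day correlation or participant-by-time variance, and say whether either is expected. If so, name the covariance structure or further random term that will be used.

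The cost is one sentence and one extra RANDOM term, with no new data. The strategy test has 29 denominator df instead of 203. If day variance is truly zero, strategy power of 80% becomes about 78% (about 76% if the variance estimate is bounded at zero), and time-by-strategy power stays at about 80%.

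### Cohen's d is planned only for significant post-hoc comparisons and no confidence interval is planned, so the size and precision of the cool-down versus rest difference in change need not be reported

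*Combined protocol and SAP*

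**What the plan says.** Section A states the aim: "we seek to determine if a vocal cool down can mitigate the negative effects of a vocally tiring task as compared to vocal rest". Section B (Cool Down versus Vocal Rest) has each participant do both strategies on different days, in counterbalanced order.

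Section J is a single paragraph. It plans a linear mixed model for each dependent measure, with four times, two strategies and their interaction: "A time and restoration strategy interaction will also be included in the model". On the random part it says: "Participant will be included as a random factor in order to control for individual variation". The follow-up is stated as "Tukey HSD tests will be used on post-hoc comparisons". The only effect-size rule is that Cohen's d "for repeated measures will be calculated on significant post-hoc comparisons". On sample size it says: "Power analysis indicates an N of 30 subjects will be sufficient to answer study questions with reasonable statistical power".

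Neither Section J nor any other section mentions a confidence interval, a standard error or a reported model estimate for any contrast.

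**The concern.** The aim concerns a difference in change: how the voice moves from before to after cool down, compared with the same movement around rest. The interaction tests this, but with four times and two strategies it is a test on (4 − 1) × (2 − 1) = 3 degrees of freedom, which yields a p-value and no size or direction. Size is left to the post-hoc stage, and there d is conditional on significance.

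Two things are at stake. For a measure without a significant result, the planned output cannot separate a difference of useful size that has been ruled out from one that was estimated too imprecisely to judge. For a measure with a significant pair, the reported d has passed a filter that favours large observed values, so on average it overstates the true difference when power is low, though not in every case.

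**Working it through.** **Stated figure.** N = 30 cannot be reproduced, because Section J gives no effect size, SD, within-person correlation or numerical power. Solving backwards for a two-sided paired t-test at 0.05 with n = 30 (29 df) gives 80% power at a d of about 0.53 and 90% at about 0.61. These are assumed readings of an unstated calculation.

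**What the Tukey comparisons cover.** Four times by two strategies make 8 cells and 8 × 7 / 2 = 28 pairs:
- same time, different strategy: 4
- same strategy, different times: 2 × 6 = 12
- different on both: 28 − 4 − 12 = 12

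A difference in change combines four cell means, so none of the 28 pairs is one.

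**Selection on significance, for one pair of means.** Assumptions not in Section J: 30 complete participants; participant as the only random term; pooled residual error with 29 × 7 = 203 df; two-sided tests; d = mean difference / SD of that pair's differences. The Tukey family is not stated, so three cut-offs on t are shown: 1.972 (uncorrected), 2.590 (Tukey, 4 means) and 3.063 (Tukey, 8 means). Each scenario had 100,000 simulated trials. Cells with three entries follow that order.

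| True d | Mean d, no selection | Power | Mean reported d | Part due to selection |
|---|---|---|---|---|
| 0.3 | 0.308 | 0.372 / 0.175 / 0.081 | 0.499 / 0.588 / 0.661 | 0.192 / 0.280 / 0.353 |
| 0.5 | 0.514 | 0.777 / 0.559 / 0.375 | 0.586 / 0.647 / 0.706 | 0.072 / 0.134 / 0.192 |
| 0.8 | 0.822 | 0.992 / 0.963 / 0.904 | 0.826 / 0.838 / 0.858 | 0.004 / 0.016 / 0.036 |

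The share of comparisons that get no d is 1 minus power: about 63% / 83% / 92% at 0.3, 22% / 44% / 62% at 0.5, and 1% / 4% / 10% at 0.8. At a true d of 0.5, the proportion of reported values at or below the truth is 0.345 / 0.142 / 0.025. The no-selection column carries about 3% ordinary small-sample bias, which is separate from the point made here.

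**Cross-check by another route.** Separate paired t-tests with 29 df, uncorrected, give mean reported d of 0.51, 0.60 and 0.83 for true values of 0.3, 0.5 and 0.8.

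**Precision of the difference in change.** It combines four cell means, so with residual SD σ:
- SE = σ√(4/30) = 0.365σ
- 95% half-width = 1.972 × 0.365σ = 0.720σ
- SD of one participant's difference in change = 2σ, so the half-width is 0.720 / 2 = 0.360 of that SD

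For one pair, SE = σ√(2/30) = 0.258σ and the half-width is 0.509σ. With 29 df instead of 203, the half-width in SDs of the difference is about 0.37.

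**The case against.** The strongest reply is that the same-time pairs already address the question. Two of the four, after the restorative strategy and after exertion task 2, fall after the strategies diverge. With counterbalanced order, the expected difference between strategies before that point is zero unless there is differential carryover or order imbalance. Such a pair then estimates the cool-down versus rest effect, and with participant as the only random term it does so more tightly: 0.51 against 0.72 residual SDs. This is correct as far as it goes. A difference in change could do better if day-to-day variation is large, but that is a modelling choice. The point survives because these pairs too get no interval, and get d only if significant.

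Second, the bias figures are for pairs of means, and they depend on which SD standardises d. If it is the raw-score SD with within-person correlation r, the value on the scale used here is raw d / √(2(1 − r)). At r = 0.8, a raw d of 0.5 becomes 0.5 / √0.4 = 0.79, close to the 0.8 row, where selection matters little. At low r the bias is larger. This stands as a limit on the size of the bias; it does not touch the missing interval.

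Third, Section J is a short plan that does not forbid estimates or intervals, and the mixed model would readily supply them. That is true, and it is why the claim is only that they need not be reported. But the one effect-size rule that Section J does state selects on significance.

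**Conclusion.** The concern holds. As written, the plan produces effect sizes selected on significance, no intervals, and no commitment to an estimate of the difference in change that the aim is about. The absence of an interval and of that commitment rests on the text alone.

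The size of the upward bias is conditional. Under the assumptions above it ranges from negligible at a true d of 0.8 to roughly a doubling (0.66 for a true 0.3) when the effect is small and Tukey covers all 8 cells. Because Section J does not quantify power, where the trial lies in that range is unknown. If true effects are about 0.8 or larger, the main loss is the missing interval. Estimation and interpretation are affected; the validity of the tests is not. The change should be made, since it bears on the stated question and costs almost nothing.

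**What to change.** In Section J, keep Cohen's d for the pairwise post-hoc comparisons but delete the word *significant*, and add:

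> For every dependent measure, the cool-down minus vocal-rest difference in change (post exertion task 1 to post restorative strategy, and baseline to post exertion task 2) will be estimated from the time-by-strategy terms and reported with its 95% confidence interval and Cohen's d, whatever its p-value.

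State which SD standardises d, and whether these intervals are adjusted for multiplicity, since they will stand beside Tukey-adjusted tests.

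The cost is SAP wording, contrast statements in the SAS model already planned, and a longer results table. No further data or participants are needed, and every pairwise d now planned is kept. The roughly 3% small-sample bias in d remains.
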